Our composite equation assumes a linear trajectory across time, based on our hypothesis of maintaining steady improvement in depression severity throughout the 12-week study period. This assumption may not be true given the timing and number of BA-PC sessions. We propose two alternative theory-driven models to capture an immediate effect from BA and possibly an effect that may weaken during subsequent weeks. Exploratory graphical methods such as subject specific outcome trajectory plots and transformations will be used to assess the linearity (or lack thereof) across time. Non-constant trajectories such as a quadratic time effect and piecewise-linear (PWL) models will be explored to determine the most parsimonious model. Since a linear time model is nested within a quadratic, the likelihood ratio (difference in -2log-likelihood) test can be used to test model fit. In the case where a quadratic provides a better fit than a linear model, consideration will be given to the magnitude of the quadratic effect as well as parsimony. Since a constant rate of change model is not nested within the PWL model, log-likelihoods cannot be compared to assess model fit. However, the Akaike Information Criterion (AIC) statistic (-2LL + 2*# of parameters) can be used to assess fit among non-

nested models. Below is a composite equation that includes two time segments (TS1, TS2) as well as cross-level interactions between time segment and group.

$$Dep_{ij} = \underbrace{\gamma_{00} + \gamma_{01}Group_i + \gamma_{10}TS1_{ij} + \gamma_{20}TS2_{ij} + \gamma_{11}Group_i * TS1_{ij} + \gamma_{21}Group_i * TS2_{ij}}_{\text{Fixed}} + \underbrace{\mu_{oi} + \mu_{1i}TS1_{ij} + \mu_{2i}TS2_{ij} + \varepsilon_{ij}}_{\text{Random}}$$

(d) The above models will be especially useful for assessing sustainability of long-term improvement up to 24 weeks after randomization. An issue of analyzing long-term follow-up data is the rate of “missingness”. Methods described below pertaining to missing data will be inspected and, if plausible, used in conjunction with MLM to compare rates of improvement between the primary 12-week study period and long term follow-up. If the reliability of estimates during the long-term follow-up period are poor due to a high rate of missing data, simple means and confidence intervals will be calculated and used for descriptive purposes.

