Aim 2: To evaluate Veteran receptivity and adherence to a 4-session BA-PC. Treatment receptivity will be measured using the CSQ, BA Acceptability Interview, and patient adherence. For the CSQ given at week 6 and week 12, each of the eight items will be summarized by calculating the proportion of patients selecting a 3 or 4 (excellent) within each randomized group. Also, the average summary score and 95% CI at week 6 and 12 will be calculated within the TAU and BA-PC group. For the Likert-scaled items on the BA Acceptability Interview, the mean and 95% confidence interval will be calculated to help summarize participant’s receptivity to BA-PC in primary care. For qualitative questions on the BA Acceptability Interview, two raters will read each participant’s response and will summarize the responses¹¹⁴. Then, the two raters will discuss the summary responses they each identified and will reach a consensus that will inform the format and feasibility of BA-PC. As mentioned in the methods, a measure of patient adherence will be collected at each intervention session (i.e., proportion of the number of goals completed versus the number of goals identified as homework by the interventionist and patient at the end of each session) allowing for an overall patient adherence to be calculated and used as an indirect reflection of patient receptivity.

Aim 3 (a): To evaluate the effectiveness of a 4-session BA-PC in reducing SI

We plan to compare the presence and severity of SI between TAU to BA-PC using MLM for the purpose of generating robust effect size estimates. While p-values are inherently provided by statistical software packages, our emphasis is to calculate means and standard errors at each time point and within each group, thereby focusing on the magnitude of effects, not statistical significance. As alluded to in the Power Analysis section, this study is not necessarily powered for detecting differences in suicidal ideation among groups.

However, SI is relevant to depression and thus will be summarized for exploratory purposes using the most powerful statistical method (e.g. MLM, GEE) given the data characteristics.

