Note on Missing Data: One of the advantages of the proposed analytic method is the handling of incomplete outcome data without resorting to listwise deletion of participants. Our analytic method provides unbiased parameter estimates under a missing at random (MAR) assumption. Unfortunately, the validity of MAR cannot be determined from the data. If the MAR assumption does not seem tenable, pattern-mixture models can be used to obtain valid parameter estimates by classifying participants into nominal categories according to the pattern of "missingness"¹¹⁵. This nominal variable is then used as a predictor of the response. The associated regression coefficient and the parameter estimates of its interaction with other predictor variables quantify how the predictor-response association differs across the patterns of missing data. For example, a model consisting of a main effect for time, a main effect for the nominal missing data pattern variable and an interaction term will inform us if baseline depression and depressive symptom trajectories differ according to the type of "missingness". Overall population estimates can be calculated by averaging over the patterns of missing data¹¹⁵ and then statistically compared between groups¹¹⁶. A nice example of using a random-effects pattern-mixture model applied to a two group longitudinal study is shown in Hedeker and Gibbons¹¹⁰.

Patient Safety

Veterans with moderate-severe symptomatology who are eligible to participate in the study may inadvertently delay treatment to remain in the study during the treatment period (12 weeks). As a result, research staff will provide patients a thorough summary of the psychological and pharmacological options for services available to them at the end of the telephone screening session. [name] will assist in linking the Veteran to those services if the patient is interested. At any time during the initial 12-weeks of the study, if the patient indicates interest in seeking psychotherapy, the research staff will immediately help the Veteran with a referral and ask whether the Veteran would consider continuing the assessment portion of the study. In addition, the consent form thoroughly reviews this information.

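### Aim 1(d): when week-24 data are sparse, the plan falls back on simple means, which are biased under the dropout its multilevel model is meant to handle

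*Combined protocol and SAP*

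**What the plan says.** Under Data Analysis and Statistical Considerations, Aim 1 offers a straight-line MLM for PHQ-9 and, as an alternative, a piecewise-linear one that "includes two time segments (TS1, TS2) as well as cross-level interactions between time segment and group". The week of the knot is not given. Part (d) then says: "The above models will be especially useful for assessing sustainability of long-term improvement up to 24 weeks after randomization". The missing-data methods are to be combined with the MLM if plausible.

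The fallback follows. Its trigger begins "If the reliability of estimates during the long-term follow-up period are poor", and where the estimates "are poor due to a high rate of missing data, simple means and confidence intervals will be calculated and used for descriptive purposes". There is no threshold. The text does not say which patients the means cover, or whether the MLM estimates would still be shown.

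The Note on Missing Data credits the MLM with "handling of incomplete outcome data without resorting to listwise deletion of participants", and adds: "Our analytic method provides unbiased parameter estimates under a missing at random (MAR) assumption". If MAR looks untenable, it offers pattern-mixture models.

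For suicidal ideation, Aim 3(a) shows that description and modelling can go together. It compares the arms "using MLM for the purpose of generating robust effect size estimates" and says "our emphasis is to calculate means and standard errors at each time point and within each group".

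**The concern.** A simple mean of the patients seen at week 24 is a complete-case mean. It discards up to seven earlier PHQ-9 scores per patient (weeks 0 to 12), and those scores are what make MAR plausible. In general it is unbiased only when missingness is unrelated to outcome within the arm. The plan thus abandons its own missing-data argument in the situation that the argument was written for.

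The situation is realistic: Study Population already allows for 30% attrition by week 12. If patients who are doing worse leave, those who remain make each arm look better at week 24 than it is. Since Aim 1(d) is about durability, these means would be read as the answer, whatever label they carry.

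**Working it through.** **What the documents supply.** 72 patients per arm; PHQ-9 at weeks 0, 2, ..., 12 and 24; 30% attrition to week 12. They give no figure for the week-24 analysis to reproduce, and no SD, week-24 attrition rate or dropout mechanism. Everything else below is assumed.

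**Why simple means are off.** Let π be a patient's probability of being observed at week 24, given the data. Then

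E(Y24 | observed) − E(Y24) = Cov(Y24, π) / E(π).

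This is zero if π is unrelated to Y24. If higher (worse) scores lower π, the covariance is negative and the simple mean is too low.

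**Assumptions, main set.**
- Means: 15 at baseline in both arms, linear to 12.0 (TAU) and 9.5 (BA-PC) at week 12, then flat. The true week-24 difference is 9.5 − 12.0 = −2.5.
- Independent random intercept, first-segment slope and second-segment slope with SDs 3.2, 0.22 and 0.10; residual SD 2.7. Week-24 variance = 3.2² + (12 × 0.22)² + (12 × 0.10)² + 2.7² = 10.24 + 6.97 + 1.44 + 7.29 = 25.94, so SD = 5.09.
- Monotone dropout: logit hazard = a + 0.8 × (last observed PHQ-9 − 12)/5, with 30% missing at week 12.
- Missing at week 24: 30% (no further loss), 40%, or 1 − 0.7² = 51% (same weekly rate). Observed per arm: 72 × 0.70, 72 × 0.60 and 72 × 0.49, about 50, 43 and 35.

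**Same MAR rule in both arms, SD 5.1** (bias from 150,000 simulated patients per arm; coverage from 500 trials of 72 per arm at each rate):

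| Missing at week 24 | Simple arm mean too low by | Coverage of its 95% CI |
|---|---|---|
| 30% | 0.6–0.7 | 83–88% |
| 40% | 0.9–1.1 | 75–78% |
| 51% | 1.2–1.5 | 59–70% |

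The two-segment MLM covers 93–96%. The difference between simple means moves only 0.1–0.3 points, because most of the error cancels.

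**Other SDs.** At 30% and 51% missing the errors are 0.4–0.5 and 0.9–1.1 (SD 4.6), and 1.0–1.2 and 1.9–2.3 (SD 6.4).

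**Weaker dependence.** With half the dropout slope (0.4) at SD 5.1, the errors are about 0.4, 0.55 and 0.73.

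**Score-related dropout in one arm only, SD 5.1** (true difference −2.5):

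| Missing at week 24 | BA-PC only | TAU only |
|---|---|---|
| 30% | −3.1 | −1.8 |
| 40% | −3.4 | −1.5 |
| 51% | −3.8 | −1.1 |

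The two-segment MLM stays within 0.05 of −2.5.

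**A second set of assumptions** (SDs 4.6, 5.5 and 6.3 at weeks 0, 12 and 24; week 12–24 correlation 0.62; 72 per arm; 250–300 trials per scenario). With dropout slope 0.35 and about 42% missing, simple means are too low by 0.73 (TAU) and 0.65 (BA-PC). With slope 0.7 and 59–65% missing, by 1.92 and 1.70. The MLM with knot at week 12 is within 0.16 throughout. Under purely random loss neither method is biased.

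**Does the fallback cure imprecision?** No. Under random loss in the main set the MLM interval is 7%, 10% and 14% narrower at 30%, 40% and 51% missing. In the second set the SD of the estimated difference is 1.27–1.69 for simple means and 1.17–1.55 for the MLM.

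**Where the MLM fails.**
- A single straight line gives a difference of −3.1 against −2.5 even with no missing data.
- In the second set, a knot at week 6 when the true bend is at week 12 puts the arm means off by −0.32 and −0.93 and the difference off by −0.61.
- If week-24 loss depends on the unseen week-24 score (SD 5.1; 40% and 51% missing), MLM means are too low by 0.2–0.3 and 0.4–0.5, against 1.1–1.3 and 1.5–1.9 for simple means.

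**The case against.** The fallback is conditional, descriptive, confined to one sub-aim and never tested. The text does not say that the MLM estimates are withheld. Pattern-mixture models are already provided for, and patients may stop the intervention yet continue assessments, so stopping treatment need not mean a missing score. The 30% case may never trigger the fallback, the 51% is an extrapolation, and the main figures rest on one assumed dropout slope. Under a common mechanism the arm difference barely moves, and nothing in the documents suggests dropout tied to score in one arm only. The MLM is not safe by default: the plan gives no knot, and week 24 is the only visit after week 12. MAR is also weakest there, because additional psychological treatment is allowed after week 12. Finally, Aim 3(a) is descriptive because of limited power, not missing data.

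Much of this stands as a limit on size and scope: the sizes are illustrative, weaker dependence roughly halves them, and the model must be specified with care. It does not rescue the rule. A descriptive label does not remove bias from the arm means, and silence about whether MLM means are still shown is itself a reason to amend. Doubt about MAR does not favour simple means, which need a stronger assumption and were further off in the not-at-random case examined. Aim 3(a) still shows that a descriptive purpose is compatible with model-based means.

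**Conclusion.** The concern holds. Followed as written and read naturally, the rule gives week-24 arm means that are too favourable whenever worse-scoring patients leave. The direction is general; the size, about 0.6 to 1.5 PHQ-9 points per arm in the main set, depends on the assumed SD, week-24 attrition and strength of dependence on score. The between-arm comparison is materially distorted only if dropout differs by arm. The MLM's advantage requires a mean model that fits week 24 and, for freedom from bias, MAR. This is a change that should be made, but it is not critical: it concerns the long-term follow-up alone.

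**What to change.** Replace the fallback sentence in Aim 1(d) with a rule along these lines:

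- Whatever the week-24 missingness, report the week-24 PHQ-9 mean in each arm and the difference, with 95% CIs, from the likelihood-based MLM fitted to all PHQ-9 visits.
- Use the two-segment model with the knot fixed at week 12, or categorical visits; do not use a single straight line.
- If the intervals are wide, report them as they are and label the estimates descriptive.
- Show simple means only as a supplement, with the number observed per arm.
- Optionally, apply the pattern-mixture approach at week 24 as a sensitivity analysis. It needs a stated assumption about the second-segment slope of patients who miss week 24, because no other visit after week 12 informs it.

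The cost is one or two SAP sentences and a few extra model runs, with no new data. The price is that week-24 intervals may be wide, and the estimates still depend on MAR and on the mean model.

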Levels of Environmental Reward will be assessed using the *Environmental Reward Observation Scale (EROS)*¹⁰⁶, which is a 10-item 4-point Likert scale that assesses the positive affect and reward associated with environmental experiences. It has been found to have strong internal consistency and test-retest reliability¹⁰⁶. It is frequently used within studies examining behavioral activation since levels of environmental reward associated with activities is a focus of the BA-PC interventions. The total score on the EROS will be used as a secondary outcome measure.

Brief Pain Inventory (BPI). The BPI (Cleeland, et al., 1994) is a widely used self-report measure that assesses pain intensity (e.g. severity, location, chronicity) and pain-related functional disability (e.g. work, relationships with others). The BPI includes 11 items that can detect significant changes in pain severity in longitudinal analyses (Kroenke, et al., 2009). The BPI has been widely validated, showing good reliability and construct validity (Tan et al., 2004).

Tobacco Use Questionnaire. This is a brief, 11-item questionnaire comprising an assessment of current smoking status, nicotine dependence via the Fagerström Test for Nicotine Dependence (FTND)¹³¹, and readiness to quit smoking.

Biweekly Assessments

Depressive symptoms will be assessed using the PHQ-9 and item #9 will be used to assess suicidal ideation for safety purposes.

Antidepressant Medication Changes will be assessed by asking the Veteran whether he/she is

continuing to take the specific dosage of the antidepressant medication daily they reported taking at baseline. If not, information will be gathered to identify whether they have decreased the medication, stopped the medication, or increased the medication.

6, 12, and 24 Week Assessments

Treatment Satisfaction and Acceptability will be assessed with two instruments.

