Therapeutic Alliance will be assessed using the Working Alliance Inventory (WAI)¹²⁹. The WAI is a 12-item self-report measure that assesses three different domains of the therapeutic alliance, including agreement on therapeutic tasks, agreement on goals of therapy, and development of a therapeutic bond.

Table 1. Schedule of Assessment Measures

SUBJECTIVE ASSESSMENTS	Time (weeks)							
	0	2	4	6	8	10	12	24
	P	T	T	T	T	T	P	T
1. Symptoms of Depression								
a. PHQ-9*	X	X	X	X	X	X	X	X
2. Intensity of Suicidal Ideation								
a. SSI	X			X			X	X
3. Quality of Life								
a. SF-12	X			X			X	X
b. QLI	X			X			X	X
4. Insomnia Severity								
a. ISI	X			X			X	X
5. Symptoms of PTSD								
a. PTSD-CL	X			X			X	X
6. Symptoms of Anxiety								
a. GAD-7	X			X			X	X
7. Level of Reward/Positive Affect from Experiences								
a. EROS	X			X			X	X
8. Pain								
a. Brief Pain Inventory	X			X			X	X
9. Patient Adherence**								
10. Treatment Receptivity								
a. Client Satisfaction Questionnaire				X			X	

b. BA Acceptability Interview***	X
11. Therapeutic Alliance	X
a. WAI	X
12. Mental Health Treatment	
a. Medication and Treatment History Questionnaire*	X X
c. Medication and Treatment via CPRS*	X X
13. Tobacco Use	
a. Tobacco Use Questionnaire	X

Note. P=in person assessment; T=telephone assessment

*These measures are also given in the initial telephone screening assessment.

**This is calculated after session 2, 3, and 4 of BA-PC

***This measure will be administered at the last BA-PC session and sealed in an envelope to allow for confidentiality and for other research staff to stay blind to condition.

Data Analysis and Statistical Considerations

The data analytic strategy emanates from the primary aim and is in line with the method used to estimate the sample size necessary to adequately test the primary hypothesis. Initial analyses will be conducted using a series of 2 (Condition: TAU vs. BA-PC) vs. 2 (Time: baseline, week 12) repeated measures ANOVAs. The primary analysis will be conducted using the intent-to-treat approach; participants who are randomized will be analyzed according to their assigned group regardless of amount of treatment received. The data will be screened for missing cases, outlier scores, and non-normal response distributions. Assumptions underlying statistical models will be assessed by examining standardized residuals, influence diagnostics and homogeneity of variance (e.g. among groups).

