Aim 1 (a, d): To evaluate the efficacy of a BA-PC in reducing depressive symptoms compared to TAU.

MLM will be used to test the primary null hypothesis that no differences exist in the rate of change in depressive symptoms measured by the PHQ-9 between BA-PC and TAU against the two-sided alternative that differences do exist. A composite equation consisting of within and between person effects will be used to analyze our data. The within-person (level 1) equation estimates participants' unique intercept (time=0) and outcome trajectory. The between-person (level 2) equation estimates the average initial status (e.g., week 0 PHQ-9 total score) and rate of change in the primary outcome (e.g., PHQ-9 total score). If the alternative hypothesis is confirmed, there would be a significant cross-level interaction between group and time of assessment suggesting a greater rate of improvement across time among participants randomized to BA-PC condition relative to TAU.

Below is the multi-level composite equation that will be utilized to model depressive symptom severity. The true depression score for the i^{th} person at the j^{th} time point is a linear combination of a between-subject main effect for group, a main effect for time, and a cross-level interaction term between group and time allowing for the fixed effect slope estimate to vary between groups. Random effects include an intercept and slope. Both level-1 and 2 (subject) residuals are assumed to be normally distributed.

$$Dep_{ij} = \underbrace{\gamma_{00} + \gamma_{01}Group_i + \gamma_{10}Time_{ij} + \gamma_{11}Group_i * Time_{ij}}_{Fixed} + \underbrace{\mu_{oi} + \mu_{li}Time_{ij}}_{Random} + \varepsilon_{ij}$$

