While eligibility criteria require a stable history of depressive medication use or non-use, patients may change (drop, add) medications during the twelve week study period. While randomization should equalize patient characteristics between groups and other research has found it has no effect on the relationship between BA and changes in depressive symptoms^{74, 79}, medication change during the course of the trial will be assessed and if necessary it can be examined as a time-varying variable. If a sufficient number of patients are on two or more medications during the course of this trial, we will assess the association (i.e. linear vs. nominal) between the number of medications and depressive symptoms using the likelihood ratio test. Then, the number of depressive medications (in stacked format) will be entered into our model primarily to adjust the other coefficients (time, time*group) for the potential confounding effect on the rate of change in depressive symptoms between groups, due to medication.

Aim 1 (b): To evaluate the efficacy of a 4-session BA-PC in improving other secondary subjective outcomes compared to TAU. Similar to our primary depression outcome, secondary outcomes (i.e., sleep, quality of life, level of environmental reward from experiences) measured at baseline, week 6, and 12 will be analyzed by forming a MLM.

Aim 1 (c): To evaluate a higher level of treatment engagement. For the number of treatment sessions completed, non-parametric methods, such as Kolmogorov-Smirnov, will be used to examine differences between BA-PC and TAU conditions. For those participants continuing to experience moderate-severe symptoms at week 12, we will use chi-square techniques to examine rates of engagement in specialty care using data collected at 24 weeks.

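### The Aim 1 medication paragraph would adjust the primary group-by-time term for medication taken after randomisation, on undefined triggers, and no sentence keeps the unadjusted model primary

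*Combined protocol and SAP*

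**What the plan says.** All of this stands in Data Analysis and Statistical Considerations unless noted.

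- **Primary model, Aim 1 (a, d).** "MLM will be used to test the primary null hypothesis that no differences exist in the rate of change in depressive symptoms". The equation has fixed effects for group, time and group-by-time, plus a random intercept and slope. It has no medication term. The group-by-time coefficient is the primary test.
- **Intent-to-treat sentence, opening paragraph.** "participants who are randomized will be analyzed according to their assigned group regardless of amount of treatment received".
- **Medication paragraph, end of Aim 1 (a, d).** It expects randomisation to balance patient characteristics and states that "other research has found it has no effect on the relationship between BA and changes in depressive symptoms". It then says that "medication change during the course of the trial will be assessed and if necessary it can be examined as a time-varying variable". A second condition follows: "If a sufficient number of patients are on two or more medications during the course of this trial", the association of the count with symptoms is tested as linear or nominal by a likelihood ratio test. Then the count, in stacked (per-visit) form, "will be entered into our model primarily to adjust the other coefficients (time, time*group) for the potential confounding effect on the rate of change".
- **Medication data.** The biweekly item asks whether the Veteran still takes "the specific dosage of the antidepressant medication daily they reported taking at baseline". It continues: "If not, information will be gathered to identify whether they have decreased the medication, stopped the medication, or increased the medication". The Assessments section adds tracking of non-study care by research assistants, and chart review at baseline, 12 and 24 weeks. Under Measures, the Medication and Treatment History questionnaire is repeated at 12 and 24 weeks.

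**The concern.** The coefficients to be adjusted, time and time-by-group, are those of the primary model, so the adjustment falls on the primary test. The plan calls the reason confounding. A variable that changes after allocation cannot be a cause of allocation. It can be a consequence of the arm or of the symptoms that the trial measures. Conditioning on it moves the estimate from the effect of being assigned to BA-PC towards an effect with medication held fixed. That is a different quantity from the one the intent-to-treat sentence implies.

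The step also depends on two conditions with no count, percentage or test attached. Whether the primary contrast is adjusted could therefore be settled after the data are seen.

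**Working it through.** **1. The passages side by side.** The intent-to-treat sentence fixes who is analysed in which arm and is silent on covariates. The primary equation is medication-free. The medication paragraph moves from a permissive verb for examining change to a firm statement that the count goes into the model. It does not call the result secondary, supportive or a sensitivity analysis. Elsewhere the plan does label lesser analyses: suicidal ideation under Aim 3 is exploratory, and unreliable long-term estimates under Aim 1 (d) are descriptive.

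**2. What the two models estimate.** Let β be the 12-week BA-PC effect with medication held fixed, δ the effect of an added drug, and p_B and p_T the proportions who have added one by week 12 in BA-PC and TAU.

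- Effect of assignment (unadjusted model): β + δ(p_B − p_T)
- Adjusted model, if its drug coefficient is close to δ: about β
- Adjusted minus unadjusted: about −δ(p_B − p_T)

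The plan gives no figure to reproduce here, and no PHQ-9 SD, drug effect, onset or start rate. All inputs below are assumptions. With β = −2.5, δ = −2, 144 patients, seven visits and complete data (1,000 simulated trials per row):

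| Added a drug, TAU / BA-PC | Formula for unadjusted | Unadjusted | Adjusted | Shift |
|---|---|---|---|---|
| 21.8% / 21.8% | −2.5 + (−2)(0) = −2.50 | −2.481 | −2.480 | 0.00 |
| 34.4% / 29.9% (same rule, driven by last score) | −2.5 + (−2)(0.299 − 0.344) = −2.41 | −2.427 | −2.522 | −0.095 |
| 35.1% / 11.5% | −2.5 + (−2)(0.115 − 0.351) = −2.03 | −2.038 | −2.506 | −0.47 |
| 11.5% / 35.2% | −2.5 + (−2)(0.352 − 0.115) = −2.97 | −2.977 | −2.497 | +0.48 |

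The shift depends on the difference in starts between arms and can go either way.

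**3. With the count coded as the plan describes** (drugs at baseline plus any added). Assumed: baseline mean 15.5, intercept SD 3.5, slope SD 0.20 per week, residual SD 2.8, TAU slope −0.25 per week, BA-PC effect −2 at week 12, 40% on one drug at entry, at most one drug added, and starts triggered by the last PHQ-9. Absolute shifts in PHQ-9 points for δ = −3:

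| Starts, TAU / BA-PC | Immediate onset | 6-week onset | Direction |
|---|---|---|---|
| 32% / 28%, same rule | 0.09 | 0.05 | favours BA-PC |
| Other common rules and variance inputs | at most 0.15 | at most 0.07 | |
| 32% / 23% | 0.18 | 0.10 | favours BA-PC |
| 42% / 10% | 0.61 (0.46–0.68 over variance inputs) | 0.34 (0.24–0.35) | favours BA-PC |
| 17% / 42% | 0.49 | 0.27 | against BA-PC |

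With no drug effect the shift is below 0.01. With δ = −2, the same-rule shifts are 0.06 and 0.03, and the 42% / 10% shifts are 0.40 and 0.23. Nominal coding changes the shift by 0.03 or less.

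**4. Sensitivity to who is medicated at entry.** One coefficient serves both baseline users and new starters. When baseline users score like non-users, that coefficient is diluted: 0.61 / 0.32 = 1.9, not 3. If baseline users enter 3 points lower, the dilution goes (0.97 / 0.32 = 3.0) and the shifts at δ = −3 grow. The same rule gives 0.12–0.16 (immediate) and 0.08–0.11 (6-week). The 42% / 10% gap gives 0.84–0.97 and 0.52–0.73.

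**5. Scale.** With 72 per arm and 30% attrition, the standard error of the 12-week difference under these variances is about 0.75 (0.65–1.08). Then 0.16 / 0.75 = 0.21 SE, 0.61 / 0.75 = 0.81 SE and 0.97 / 0.75 = 1.29 SE. The shifts come from complete data and the SE allows for attrition, so the ratios are only a rough guide.

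**The case against.** The best defence is that the plan already indicates a default. It ties the primary hypothesis to a medication-free equation, expects balance, cites research finding no medication effect, and speaks of examining medication change only where needed. This stands as a reading of intent. It does not settle the matter, because once the condition is met the count goes into that same model, and no sentence says which estimate is then primary.

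A second defence is that the count includes week 0, so part of it precedes randomisation. That is true, and that part does no harm. The difficulty lies in what changes afterwards.

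Third, the magnitudes are all assumed, and those under a common start rule are small. That also stands.

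Three stronger readings are tempting and not supported:

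- **That the adjusted model is the intended primary analysis.** The hedged wording points the other way.
- **That medication starts will differ by arm.** Nothing shows this. Under Patient Safety, pharmacological options are summarised for every patient at telephone screening, before randomisation.
- **That a medication count cannot be built.** The biweekly item alone covers only the baseline drug, but tracking of non-study care, chart review and the treatment history questionnaire may supply more. What is missing is a statement of which source feeds the count at each visit.

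**Conclusion.** The concern holds in this form: as written, a triggered medication adjustment would change what the primary group-by-time term estimates, under a mistaken label of confounding, and no sentence keeps the unadjusted estimate primary. That conclusion rests on the text and needs no large shift.

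The size is unknown from the documents. It is essentially nil without a drug effect and about 0.15 points at most under a common start rule (0.16 if baseline users enter lower). It reaches a few tenths to nearly 1 point only under assumed large between-arm gaps in starts, in either direction. This is a cheap improvement to the plan. It is not evidence that the result will be biased.

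**What to change.** Add to Aim 1 (a, d):

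1. The primary group-by-time test comes from the stated multilevel model, with whatever time form is chosen under the linear, quadratic or piecewise procedure already described, and with no post-randomisation medication covariate, whatever medication changes occur.
2. The time-varying medication model is supportive and does not replace the primary estimate.
3. Its trigger is given as a number or rule, its coding (linear or nominal) is fixed in advance, and the source of the count at each visit is named from the biweekly item, the tracking of non-study care, chart review and the treatment history questionnaire.

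Adjusting the primary model for baseline antidepressant status is optional; it is already collected.

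The cost is a few sentences of analysis-plan wording, with no change to sample size or conduct and no new data for the primary analysis. The supportive model has to work with the medication data the trial already records. The downside is that the medication-adjusted estimate is reported only as supportive.
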